8.3.2.8. Mini-Mental State Examination

The MMSE ([Folstein et al, 1975](#)) consists of 11 tests of orientation, memory (recent and immediate), concentration, language, and praxis. Scores range from 0 to 30, with lower scores indicating greater cognitive impairment. It is based on the performance of the subject and takes approximately 5 to 10 minutes to administer.

8.3.2.9. Montreal Cognitive Assessment Scale

The Montreal Cognitive Assessment (MoCA) scale (Nasreddine et al, 2005) is designed to assess different cognitive domains: attention and concentration, executive functions, memory, language, visuo-constructional skills, conceptual thinking, calculations, and orientation. Ongoing work with Biundo et al (2016) and others suggests that, in PD and DLB, MoCA is more sensitive to detect the earliest stage; whereas MMSE is more sensitive in the more advanced stage, leading to a recommendation by the EU Joint Programme – Neurodegenerative Disease Research (JPND) Working Group on Longitudinal Cohorts that both measures be included in studies of these patient populations. Time to administer the MoCA is approximately 10 minutes. The total possible score is 30 points; a score of 26 or above is considered normal. To reduce practice effects, different versions of MoCA will be used across visits.

8.3.2.10. Pregnancy

The study will allow female subjects who are postmenopausal for at least 24 consecutive months who have undergone surgical removal of the uterus or both ovaries.

8.3.3. Pharmacokinetic Assessments

Two blood samples for PK analysis of plasma nelotanserin and M1 metabolite concentration will be collected at the time points indicated in the Time and Events Schedule (Table 2).

The actual date and time of each blood sample collection, and the date and time of the last dose of study treatment taken prior to pharmacokinetic sampling will be recorded.

Processing, storage and shipping procedures are provided in the laboratory manual.

Plasma analysis will be performed under the control of the Sponsor. Concentrations of nelotanserin and M1 metabolite will be determined in plasma samples using the currently approved bioanalytical methodology. Raw data will be archived at the bioanalytical site.

Once the plasma has been analyzed for nelotanserin and M1 metabolite, any remaining plasma may be analyzed for other additional compound-related metabolites and the results reported under a separate protocol.

8.3.4. Data Monitoring Committee

A Data Monitoring Committee (DMC) will review the clinical and laboratory safety data at the frequency noted in the DMC Charter. The DMC will make a recommendation based on its review of the data. Details are outlined in the DMC Charter.

9. DATA MANAGEMENT

For this study subject data will be entered onto electronic CRFs and combined with data provided from other sources in a validated data system.

Management of clinical data will be performed in accordance with applicable standards and data cleaning procedures to ensure the integrity of the data, eg, correcting errors and inconsistencies in the data.

Medical histories and AEs will be coded using an agreed version of the Medical Dictionary for Regulatory Activities (MedDRA), using the Sponsor's or its representative's coding conventions.

Concomitant medications will be coded using the World Health Organization Anatomical Therapeutic Chemical classification.

The electronic CRFs will be archived (including data, queries, and audit trails) on digital media at the conclusion of the trial and will be retained by the Sponsor. In addition, individual site data will be archived on digital media and sent to the sites for their records; an acknowledgement of receipt will accompany the files.

10. STATISTICAL CONSIDERATIONS AND DATA ANALYSES

10.1. Hypotheses

The analysis of primary endpoint will test the following null hypothesis:

- The change in mean frequency per 10 minutes of REM sleep of RBD behaviors (sum of simple/major and complex RBD events) from baseline (the whole-night sleep study during placebo run-in period) to EOS (the whole-night sleep study at the EOS) will be statistically equivalent for nelotanserin and placebo treatment arms for the DLB patient subgroup.

The analysis of key secondary endpoint will test the following null hypothesis:

- The change in mean UPDRS Part III scores from baseline to EOS will be statistically equivalent for nelotanserin and placebo treatment arms for the DLB patient subgroup.
- The change in frequency per 10 minutes of REM sleep of characteristic RBD behaviors (sum of simple/minor, simple/major, and complex RBD events) from baseline (the whole-night sleep study during placebo run-in period) to end of study (EOS) (the whole-night sleep study at the EOS) will be statistically equivalent for nelotanserin and placebo treatment arms for the DLB patient subgroup

The analysis of other secondary endpoints will test the following null hypotheses:

- The change in mean UPDRS Part II scores from baseline to EOS will be statistically equivalent for nelotanserin and placebo treatment arms for the DLB patient subgroup.
- The change in mean UPDRS Parts II + III composite scores from baseline to EOS will be statistically equivalent for nelotanserin and placebo treatment arms for the DLB patient subgroup.
- The change in mean UPDRS 5-item subscale scores from baseline to EOS will be statistically equivalent for nelotanserin and placebo treatment arms for the DLB patient subgroup.
- The change in mean proportion of RBD behaviors (sum of simple/minor, simple/major and complex RBD events) rated as severe, based on video/audio assessment conducted at a sleep laboratory, from baseline to EOS will be statistically equivalent for nelotanserin and placebo treatment arms for the DLB patient subgroup.
- The change in mean score on a composite of both severity and frequency of RBD behaviors (sum of simple/minor, simple/major and complex RBD events), based on video/audio assessment conducted at a sleep laboratory, from baseline to EOS will be statistically equivalent for nelotanserin and placebo treatment arms for the DLB patient subgroup.
- The change in the mean EMG activity during REM sleep, based on PSG assessment conducted at a sleep laboratory, from baseline to EOS will be statistically equivalent for nelotanserin and placebo treatment arms for the DLB patient subgroup.
- The change in the mean number of nights with injurious behaviors to the subject or the bed partner per week, based on self or caregiver reports from the daily study diary, from baseline to EOS will be statistically equivalent for nelotanserin and placebo treatment arms

for the DLB patient subgroup.

- The change in the mean number of nights with no sleep movements per week, the mean nightly number of sleep movements per week, the mean nightly severity of sleep movements per week, and in the mean composite score based on nightly number and severity of sleep movements per week, based on self or caregiver reports from the daily study diary, from baseline to EOS will be statistically equivalent for nelotanserin and placebo treatment arms for the DLB patient subgroup.
- The change in the mean number of nights with no sleep vocalizations per week, the mean nightly number of sleep vocalizations per week, the mean nightly severity of sleep vocalizations per week, and in the mean composite score based on nightly number and severity of sleep vocalizations per week, based on self or caregiver reports from the daily study diary, from baseline to EOS will be statistically equivalent for nelotanserin and placebo treatment arms for the DLB patient subgroup.
- The change in mean SCOPA NS subscale scores from baseline to EOS will be statistically equivalent for nelotanserin and placebo treatment arms for the DLB patient subgroup.
- The change in mean SCOPA DS subscale scores from baseline to EOS will be statistically equivalent for nelotanserin and placebo treatment arms for the DLB patient subgroup.
- The change in mean VAS score for quality of bed partner sleep from baseline to EOS will be statistically equivalent for nelotanserin and placebo treatment arms for the DLB patient subgroup.
- The difference in mean CGIC-RBD score at EOS will be statistically equivalent for nelotanserin and placebo treatment arms for the DLB patient subgroup.
- The change in objective sleep parameters assessed from PSG (including but not limiting to WASO; number of arousals; SE; TST; duration and proportion of sleep time in Stage 1, Stage 2, Stage 3, and REM; latency to sleep/persistent sleep; latency to Stage 1, Stage 2, Stage 3, and REM; duration of wakefulness) from baseline to EOS will be statistically equivalent for nelotanserin and placebo treatment arms for the DLB patient subgroup.
- The change in mean nightly total count assessment from the ActiGraph activity monitor from baseline to EOS will be statistically equivalent for nelotanserin and placebo treatment arms for the DLB patient subgroup.

10.2. Sample Size Considerations

The sample size was determined based on the primary efficacy endpoints, which test for statistically significant differences between nelotanserin and placebo treatment arms in the change in frequency per 10 minutes of REM sleep of characteristic RBD behaviors (sum of simple/major and complex RBD events), based on video/audio assessment conducted at a sleep laboratory, from baseline to EOS for the DLB subgroup. Based on results of a power analysis, a sample size of 34 subjects would provide statistical power ($1 - \beta$) of 0.62 to detect a 0.8 unit treatment arm difference (ie, Cohen's $f = 0.4$) in the change from baseline to EOS in the nightly frequency of RBD behaviors measured by video/audio assessment conducted at a sleep laboratory, assuming a standard deviation of 1 unit, using an analysis of covariance (ANCOVA) model with a single 2-level between-groups fixed effect and 2 covariates and a significance level for type I error (α) of

0.05.

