Statistical Methods	
Sample Size: The sample size was determined based on the primary efficacy endpoint, which tests for statistically significant differences between nelotanserin and placebo treatment arms in the change in frequency per 10 minutes of REM sleep of characteristic RBD behaviors (sum of simple/major and complex RBD events), based on video/audio assessment conducted at a sleep laboratory, from baseline to EOS for the DLB subgroup. Based on results of a power analysis, a sample size of 34 subjects (17 subjects per treatment arm) would provide statistical power ($1 - \beta$) of 0.62 to detect a 0.8 unit treatment arm difference (ie, Cohen's $f = 0.4$) in the change from baseline to EOS in the nightly frequency of RBD behaviors measured by video/audio assessment conducted at a sleep laboratory, assuming a standard deviation of 1 unit, using an analysis of covariance (ANCOVA) model with a single 2-level between-groups fixed effect and 2 covariates and a significance level for type I error (α) of 0.05.
 
Primary Efficacy Analysis: Statistical significance of between-group differences in change in frequency per 10 minutes of REM sleep of characteristic RBD behaviors (sum of simple/major and complex RBD events) for the DLB patient subgroup, based on video/audio assessment conducted at a sleep laboratory from baseline to EOS, will be tested using univariate ANCOVA models that include treatment arm as a fixed effect and both baseline value and status (presence/absence) of background treatment with melatonin/clonazepam (or other benzodiazepines) as covariates.
 
Secondary and Exploratory Efficacy Analysis: For secondary and exploratory efficacy endpoints for which treatment comparisons of change in values will be compared across 2 time points (ie, baseline and EOS), statistical significance of between-group differences in change in mean values from baseline to EOS visits will be tested for the DLB patient subgroup, the PDD patient subgroup, and all patients using univariate ANCOVA models that include treatment arm as a fixed effect and both the baseline value of the endpoint and status (presence/absence) of background

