6. SUBJECT POPULATION

6.1. Type and Number of Subjects

The study will randomize approximately 52 subjects with DLB and PDD (with approximately 34 DLB subjects) who experience frequent RBD behaviors prior to screening and meet randomization criteria (Section 6.2.3) during 1 or more qualifying night(s) in the single-blind placebo run-in period (based on a central review of video-PSG data obtained from the sleep laboratory):

Nelotanserin 80 mg - 26 subjects

Placebo - 26 subjects.

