6.5. Withdrawal Criteria

6.5.1. Reasons for Withdrawal

A withdrawal from the study is defined as withdrawing any time after entering the single-blind placebo run-in period and before completion of the EOS visit (Visit 5). Subjects who permanently discontinue use of investigational product will be considered to be withdrawn from the study. Subjects may withdraw from the study at any time and for any reason. The investigator (or designee) must document the reason for withdrawal in the Study Conclusion section of the case report form (CRF). Information related to AEs will continue to be collected as per usual procedures on subjects who have discontinued investigational product. Withdrawn subjects during double-blind period will not be replaced. The reasons for subject withdrawal will be recorded and may include, but are not limited to:

- Any clinical AE, laboratory abnormality, or other medical condition or situation occurs such that continued participation in the study would not be in the best interest of the subject in the opinion of the investigator
- Significant protocol violation
- Subject requests to discontinue for any reason; it is important to determine whether the withdrawal of consent is primarily due to an AE, lack of effectiveness, or other reason
- Subjects don't meet the eligibility criteria at baseline (Visit 4)

The above reasons do not automatically lead to withdrawal from the study in all cases. The final decision will be based on consultation between the principal investigator and the study medical monitor, with the ultimate decision by the principal investigator or subject.

If a subject requires initiation of obstructive sleep apnea/central sleep apnea (OSA/CSA) treatment based on Visit 3 sleep laboratory assessments, the subject will be considered a run-in failure. After stable treatment and satisfactory adherence to treatment established for at least 2 weeks (eg, continuous positive airway pressure [CPAP] >4 hours usage nightly for at least 70% of nights or evidence of effective treatment based on patient/caregiver report), the run-in failed subject may be considered for participating in this study for the second and final time. The subject will be re-consented and assigned a new study ID.

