If a subject discontinues during the placebo run-in period, the Early Termination Visit sleep laboratory assessment will not be required, but all other early termination procedures must be performed. If a subject meets discontinuation criteria during double-blind treatment, an Early Termination Visit (including sleep laboratory) will be required.

Subjects who meet any of the following laboratory abnormality criteria will be discontinued from the study (adapted from FDA Draft 2009 Guidance for Industry Drug-Induced Liver Injury: Premarketing Clinical Evaluation):

- ALT or AST >5xULN, confirmed by immediate repeat testing
- ALT or AST >3xULN and TBL >2xULN or INR >1.5, confirmed by immediate repeat testing
- ALT or AST >3xULN, confirmed by immediate repeat testing, with a concurrent report of fatigue, nausea, vomiting, right upper quadrant pain or tenderness, fever, rash, and/or eosinophilia (>5%). If, upon repeat testing of liver chemistry, the symptoms outlined have resolved, but the liver chemistry still meet the noted criteria, subjects should discontinue study treatment.

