10.3. Data Analysis Considerations

10.3.1. Analysis Populations

The run-in population will consist of all subjects who took at least one dose of single-blind placebo dose during the run-in period.

The Randomized Safety Population will consist of all subjects who were randomized and took at least one dose of investigational product (i.e., nelotanserin or placebo) during the double-blind treatment phase.

The Full Analysis Set (FAS) will consist of all randomized subjects who took at least one dose of investigational product during the double-blind treatment phase, with evaluable baseline primary efficacy assessment, and a post-baseline primary efficacy assessment.

The Per-Protocol Analysis Set (PPAS) will consist of all subjects in the FAS who did not have any major protocol deviations.

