10.4. Key Elements of Analysis Plan

The primary objective of this study is to evaluate the efficacy of nelotanserin in reducing the nightly frequency of characteristic RBD behaviors (sum of simple/major and complex events per 10 minutes of REM sleep) following 4 weeks of treatment for patients with DLB.

Descriptive statistics for all efficacy and safety measures over the course of the study will be presented for the DLB patient subgroup, as well as for the PDD patient subgroup and the full patient sample. Continuous data will be summarized by means, standard deviations, standard errors, medians, interquartile ranges, maximum observed value, minimum observed value, and number of subjects. Categorical data will be summarized by frequency counts and proportions.

Listings will be sorted by subject and time. Summaries will be presented by treatment, disease type, and time. Version 9.2 or higher of the SAS system will be used to analyze the data as well as to generate tables, figures, and listings. Further details of analyses to be performed will be provided in the statistical analysis plan (SAP).

Analysis datasets will be constructed using version SAS 9.2 or later following current CDISC guidelines.

Missing data will not be imputed for primary analysis. If there are missing data at EOS visits for the primary or key secondary efficacy endpoints, the impact of missing data will be evaluated by testing the primary analysis model using the subset of the Randomized Safety Population who have an evaluable primary endpoint assessment at baseline, with any missing values at EOS imputed using multiple imputation. Details of imputation and any changes or refinements necessary will be documented in the SAP.

Compliance:

- Summary of treatment compliance will be presented by treatment arm. The number and percentage for compliance expressed as a categorical variable (<80%, ≥80% to ≤120%, and >120%) will also be presented by treatment arm.
- For efficacy endpoints derived based on the study diary, if subjects report values for < 50% of days during a weekly period, all daily values for that item (and thus all endpoints that are computed using that item) will be set to missing for that week.
- Efficacy endpoints assessed with ActiGraph will only be calculated for each weekly period during the run-in and double-blind treatment periods for subjects with non-missing data for at least 4 nights during that week.

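### Does the stated power of 0.62 fail because about 34 DLB subjects are both the number randomized and the number assumed in the calculation?

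*Combined protocol and SAP*

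**What the plan says.** The power statement appears twice. Section 10.2 says that "a sample size of 34 subjects would provide statistical power" of 0.62. The Protocol Summary adds the split by arm: "a sample size of 34 subjects (17 subjects per treatment arm) would provide statistical power". Both use a treatment difference of 0.8 units, a standard deviation of 1 unit (Cohen's f = 0.4), an ANCOVA with one two-level factor and two covariates, and alpha 0.05.

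The enrolment target is in Section 6.1: "The study will randomize approximately 52 subjects with DLB and PDD (with approximately 34 DLB subjects"). The Protocol Summary gives the same target.

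Three rules bear on how many of those subjects are analysed:

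- Section 10.3.1 limits the Full Analysis Set to dosed subjects "with evaluable baseline primary efficacy assessment, and a post-baseline primary efficacy assessment".
- Section 6.5.1 states "Withdrawn subjects during double-blind period will not be replaced".
- Section 10.4 states "Missing data will not be imputed for primary analysis". The same paragraph plans a repeat of the primary model with missing end-of-study values multiply imputed, to assess their impact.

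Other provisions work to keep subjects evaluable. Section 6.5.1 says "If a subject meets discontinuation criteria during double-blind treatment, an Early Termination Visit (including sleep laboratory) will be required". Section 8.1 obliges early discontinuers who took a double-blind dose to contact the site to schedule the video-PSG, and it allows up to two repeat nights when the REM requirement is not met. Section 6.5.2 asks investigators to make every effort to complete the Early Termination evaluations. Note 3 to Table 2 lets the medical monitor extend the sleep-laboratory window.

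**The concern.** A power calculation describes the subjects who enter the model. Here the number in the calculation and the number randomized are the same, about 34, and neither sample-size text mentions evaluability, dropout or inflation. The plan also says "Subjects may withdraw from the study at any time and for any reason", does not replace those who leave, and does not impute in the primary test. A DLB subject with no usable post-baseline video-PSG therefore drops out of the analysis, and the analysed number falls below 34 unless enrolment runs over.

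On that reading, 0.62 is the power with essentially no loss. The stakes would be in how a non-significant result is read. The type II error probability is already 0.38 (1 − 0.62), so someone weighing such a result would want to know whether the quoted power refers to subjects randomized or subjects analysed.

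**Working it through.** **Inputs.** Difference 0.8, SD 1, two covariates, alpha 0.05 (Section 10.2); 17 per arm (Protocol Summary); 1:1 allocation (Section 5.1). The text does not say whether the test is one- or two-sided. The F test of a two-level factor is two-sided, and a one-sided test would give 0.737, which does not match the stated figure.

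**Formula.** Power = P(F′ > F_crit), where F′ is noncentral F with 1 and N − 4 degrees of freedom (two group means and two covariates). With equal arms the noncentrality is λ = f² × N and f = 0.8 / (2 × 1) = 0.4. With unequal arms λ = 0.8² × n₁n₂ / (n₁ + n₂).

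**Reproducing the plan's figure.** N = 34: λ = 0.16 × 34 = 5.44, error df = 30, power = 0.6169. This rounds to the stated 0.62, so there is no arithmetic error, and the figure holds for 34 subjects in the model.

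**Other analysed numbers.** The documents give no loss rate, so every row except N = 34 is illustrative.

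| DLB subjects analysed | λ | Error df | Power |
|---|---|---|---|
| 36 | 5.76 | 32 | 0.643 |
| 35 | 5.60 | 31 | 0.630 |
| 34 | 5.44 | 30 | 0.617 |
| 33 | 5.28 | 29 | 0.603 |
| 32 | 5.12 | 28 | 0.589 |
| 31 | 4.96 | 27 | 0.574 |
| 30 | 4.80 | 26 | 0.560 |

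Uneven loss matters little more: 17 and 15 gives λ = 5.10 and power 0.587; 17 and 13 gives λ = 4.715 and power 0.552.

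**Scale of the effect.** Two subjects lost costs 0.617 − 0.589 = 0.028. Four lost costs 0.617 − 0.560 = 0.057. For comparison, keep N = 34 and vary the assumed SD (illustrative values). An SD of 1.03 gives λ = 0.64 × 34 / (4 × 1.03²) = 5.128 and power 0.592, close to the effect of losing two subjects. An SD of 1.1 gives λ = 4.496 and power 0.537, worse than losing four. Small errors in the assumed SD therefore matter as much as the losses in question.

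**Who is actually lost.** Withdrawal is not the same as being non-evaluable. Section 10.3.1 asks for a post-baseline primary assessment, not one on a particular day, and Sections 6.5.1 and 8.1 send early discontinuers to the sleep laboratory. Only a subject with no usable post-baseline recording leaves the primary analysis. Section 10.4.1 does not name an analysis set for the primary ANCOVA, but this makes no difference here: without imputation, a subject with no end-of-study value cannot contribute a change score.

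**Target in both directions.** If 36 DLB subjects are randomized and two are lost, 34 are analysed and power is again 0.617. An approximate target of 34 allows this as readily as it allows a shortfall.

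**The case for a change.** The case for a change is that the wording is incomplete and the repair is cheap. One clause in two places would say that 34 means evaluable subjects and could show the power at 32 and 30. The protections in Sections 6.5.1, 6.5.2 and 8.1 reduce losses without ruling them out, and Section 10.4 itself foresees missing end-of-study values. The multiple-imputation analysis assesses their impact but does not restore power to the primary test. From a starting power of 0.62, a fall to 0.56 raises the type II error probability from 0.38 to 0.44.

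Much of this stands. Neither sample-size text uses the word evaluable or states an allowance, and any net loss below 34 lowers power by the amounts shown. What does not stand is the step to a required change. The documents give no loss rate, so the design is not shown to miss its stated power, and printing values at 32 and 30 would put arbitrary numbers into the protocol. The wording is also already conditional, because it says what 34 subjects would provide. It makes no promise about 34 randomized subjects after losses.

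**Conclusion.** No change is needed. The 0.62 is correct (0.617) for 34 DLB subjects in the ANCOVA at the stated difference of 0.8, SD of 1, two covariates and two-sided alpha of 0.05. The plan leaves unsaid that 34 means subjects analysed, which a statistician will assume on reading a power statement. If losses took the analysed number to 32 or 30, power would be 0.59 or 0.56. That is a modest shift for a Phase 2 subgroup test whose sponsor has openly accepted 0.62, and it would not support a different decision about the design.

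This conclusion rests on three things: the documents give no expected loss, the target is approximate and can be exceeded, and early discontinuers are directed to a sleep-laboratory assessment that can keep them in the analysis. Inserting the word evaluable would be harmless, but it would change no test, estimand, decision rule or enrolment number, and under Section 11.2.1 it would need ethics committee submission like any other protocol modification.
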